14.1 Changes to Planned Analyses in the Protocol

Three new endpoints were added to SAP Section [3.3](#) listed as below and corresponding analyses were added to Section [9.5.7](#).

- Responder status of at least █-point improvement (increase) in MSQ v2.1 RFR score at Month 6
- Responder status of at least █-point improvement (increase) in MSQ v2.1 RFR score at Month 6
- Responder status of at least █-point improvement (decrease) in AIM-D PI score across Months 5 and 6

The efficacy subgroup analyses for age [$< 40, \geq 40$], for each race, and for prophylactic treatment failure subgroup [failed fewer than █ preventive treatments or failed at least █ preventive treatments] for the primary efficacy endpoint were added in SAP Section [9.7](#).

The safety subgroup analyses for age [$< 40, \geq 40$] and for each race for treatment-related TEAEs were added in SAP Section [10.7](#).

Appendix B. Potentially Clinically Important Criteria for Safety Endpoints

The criteria for Potentially Clinically Important (PCI) laboratory findings are described in Table B-1, Table B-2 and Table B-3 and the PCI criteria for vital sign findings are described in Table B-4.

Table B-1. Criteria for Potentially Clinically Important Hematology Values

Hematology Variables	Flag	Criteria
		Observed Value
Hemoglobin (g/L)	High	Increase in > 2 g/dL above ULN or > baseline if baseline > ULN
	Low	< 100
WBC Count ($10^9/L$)	High	-
	Low	< 3
Neutrophils ($10^9/L$)	High	-
	Low	< 1.5
Lymphocytes ($10^9/L$)	High	> 4
	Low	< 0.8
Platelets ($10^9/L$)	High	-
	Low	< 75.0

ULN Upper Limit of Normal

Note: A post baseline value must be more extreme than the baseline value to be considered a potentially clinically important finding.

Table B-2. Criteria for Potentially Clinically Important Chemistry Values

Chemistry Variables	Flag	Criteria ^a
		Observed Value
Albumin (g/L)	High	-
	Low	< 30
Alkaline Phosphatase (U/L)	High	> 2.5 × ULN
	Low	-
Alanine Aminotransferase (U/L)	High	> 3.0 × ULN
	Low	-
Aspartate Aminotransferase (U/L)	High	> 3.0 × ULN
	Low	-
Total Bilirubin (umol/L)	High	> 1.5 × ULN
	Low	-
Calcium (mmol/L)	High	Corrected serum calcium > 2.9@; Ionized calcium > 1.5
	Low	Corrected serum calcium < 2.0@; Ionized calcium < 1.0
Creatinine (umol/L)	High	> 1.5 × ULN
	Low	-
Glucose (mmol/L)	High	> 13.9
	Low	< 2.2
Potassium (mmol/L)	High	> 5.5
	Low	< LLN
Sodium (mmol/L)	High	> 150
	Low	< 130

ULN Upper Limit of Normal; LLN Lower Limit of Normal

@ Calcium corrected for Albumin (can be used if it is confirmed with the lab that the result has been corrected for Albumin and not a different protein).

a. A post baseline value must be more extreme than the baseline value to be considered a potentially clinically important finding.

Table B-3. Criteria for Potentially Clinically Important Urinalysis Values

Hematology Variables	Flag	Criteria	
		Observed Value	
pH	High	> 1.1 × ULN	
	Low	< 0.9 × LLN	
Glucose	High	At least 1 +	
	Low	-	
Protein	High	At least 1 +	
	Low	-	
Specific gravity	High	> 1.1 × ULN	
	Low	-	

ULN Upper Limit of Normal; LLN lower limit of normal value

Note: A post baseline value must be more extreme than the baseline value to be considered a potentially clinically important finding.

Table B-4. Criteria for Potentially Clinically Important Vital Sign Values

Vital Signs Variables	Criterion	Criteria	
		Observed Value	Change From Baseline
Sitting Systolic Blood Pressure (mmHg)	High	≥ 160	Increase of ≥ 20
	Low	≤ 90	Decrease of ≥ 20
Sitting Diastolic Blood Pressure (mmHg)	High	≥ 100	Increase of ≥ 15
	Low	≤ 50	Decrease of ≥ 15
Sitting Pulse rate (bpm)	High	≥ 110	Increase of ≥ 15
	Low	≤ 50	Decrease of ≥ 15

bpm beats per minute

Note: A post baseline value is considered potentially clinically important if it meets both the observed value and the change from baseline criteria.

Document Approval

Study M21307 - Statistical Analysis Plan Version 4 - 03Jun2024 (E3 16.1.9)

Version: 1.0 **Date:** 05-Jun-2024

Company ID: 20240605-0900f9f687b7e2a9-1.0-en

Signed by:	Date:	Meaning of Signature:
	05-Jun-2024 00:15 UTC	Approver - Statistics
	04-Jun-2024 19:40 UTC	Approver - Statistics
	04-Jun-2024 17:36 UTC	Approver
	04-Jun-2024 17:24 UTC	Approver
	03-Jun-2024 23:25 UTC	Author

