10.3 Analysis of Laboratory Data

The clinical laboratory tests defined in the protocol operations manual (e.g., hematology, clinical chemistry, and urinalysis) will be summarized.

Each laboratory variable will be summarized for all time points (starting with Baseline) with the number of non-missing observations, mean and standard deviation, median, minimum and maximum. Mean change from baseline to each applicable post-baseline visit will be summarized for selected laboratory variables, with the number of observations, baseline mean, and visit mean. The change from baseline mean, standard error will be presented for the mean change from baseline within each treatment group.

Changes in laboratory parameters will be tabulated using shift tables categorized as low, normal, or high based on the normal ranges of the laboratory used for each sample. A shift table will be provided to summarize shifts from baseline to post-baseline values.

Laboratory abnormalities will be evaluated based on Potentially Clinically Important (PCI) criteria ([Appendix B](#)). For each laboratory PCI criterion, the number and percentage of subjects who have a laboratory value meeting the criteria will be summarized. Listings will be provided to summarize subject-level laboratory data for subjects meeting PCI criteria. Hematology variables include hematocrit, hemoglobin, white blood cell count, neutrophils, lymphocytes, monocytes, platelet count (estimate not acceptable), blasts (if present).

Urinalysis variables include specific gravity, ketones, pH, protein, blood, glucose.

Chemistry variables include blood urea nitrogen, creatinine, total bilirubin, direct and indirect bilirubin, alanine aminotransferase (ALT), aspartate aminotransferase (AST), alkaline phosphatase, sodium, potassium, calcium, inorganic phosphorus, total protein, glucose, hemoglobin A1c, albumin, chloride, bicarbonate, creatinine clearance (Cockcroft-Gault calculation).

In addition, ALT/SGPT, AST/SGOT, alkaline phosphatase, and total bilirubin will be categorized as follows:

- $> 1.5 \times \text{ULN}$ to $\leq 3.0 \times \text{ULN}$
- $> 3.0 \times \text{ULN}$ to $\leq 5.0 \times \text{ULN}$
- $> 5.0 \times \text{ULN}$ to $\leq 10.0 \times \text{ULN}$
- $> 10.0 \times \text{ULN}$ to $\leq 20.0 \times \text{ULN}$
- $> 20.0 \times \text{ULN}$

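### The only potentially-clinically-important cut-off for urine specific gravity (> 1.1 × ULN) lies at 1.100 or above, so no plausible reading can meet it and its row in the safety table carries no information

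*SAP*

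**What the plan says.** Table B-3 in SAP Appendix B lists the urinalysis PCI criteria. The specific gravity entry is "Specific gravity High > 1.1 × ULN", and the Low entry is a dash. A note under the table adds a second condition: "A post baseline value must be more extreme than the baseline value to be considered a potentially clinically important finding".

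SAP 10.3 makes specific gravity an analysed variable ("Urinalysis variables include specific gravity, ketones, pH, protein, blood, glucose") and commits to a result for every criterion: "For each laboratory PCI criterion, the number and percentage of subjects who have a laboratory value meeting the criteria will be summarized". Subject-level listings follow for those who meet one.

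The same section plans two displays that do not use the PCI cut-off. Each laboratory variable is summarized at all time points, with minimum and maximum among the statistics. There are also shift tables: "Changes in laboratory parameters will be tabulated using shift tables categorized as low, normal, or high based on the normal ranges of the laboratory used".

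**The concern.** A multiple of the ULN works for an analyte with a true zero and room to rise several-fold. Table B-2 uses multipliers in that way for ALT, AST, alkaline phosphatase, bilirubin and creatinine. For analytes held in a narrow band it uses fixed values (sodium > 150 or < 130, potassium > 5.5) or the plain limit (potassium < LLN). Specific gravity varies over a very narrow band just above 1.000, yet it is given a multiplier. Ten percent of the raw value is then almost entirely ten percent of the water baseline, not of the part that varies.

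What is at stake is whether one row of the safety output can be read. If no value can reach the cut-off, a zero count does not distinguish a criterion that nobody met from one that nobody could meet.

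**Working it through.** The plan gives only a multiplier. It states no numeric ULN, measuring range or resulting cut-off for specific gravity, so there is no figure of the plan's own to reproduce.

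**Inputs**
- Multiplier 1.1, High only: SAP Table B-3.
- Extra condition, more extreme than baseline: note to Table B-3. It can only make the rule stricter.
- Scale anchored at 1.000: from the definition of specific gravity (density relative to water).
- ULN: not in the documents. Assumed 1.020 to 1.040, with 1.000 as the limiting case.
- Highest valid urine reading: not in the documents. Assumed ceilings of 1.040, 1.060 and 1.080 are tried.

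**Step 1: the cut-off.** Cut-off = 1.1 × ULN. Excess ratio = (1.1 × ULN − 1) / (ULN − 1), which is how far above water a flagged reading must lie compared with a reading at the ULN.

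| Assumed ULN | Cut-off | Excess at cut-off / excess at ULN |
|---|---|---|
| 1.000 | 1.100 | not defined |
| 1.020 | 1.122 | 0.122 / 0.020 = 6.1 |
| 1.030 | 1.133 | 0.133 / 0.030 = 4.4 |
| 1.040 | 1.144 | 0.144 / 0.040 = 3.6 |

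The cut-off rises with the ULN, so 1.100 is its lowest possible value.

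**Step 2: in reverse.** If the highest valid reading is M, a flag needs 1.1 × ULN < M, that is ULN < M / 1.1.

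| Assumed highest reading M | ULN needed for any flag |
|---|---|
| 1.040 | < 0.9455 |
| 1.060 | < 0.9636 |
| 1.080 | < 0.9818 |

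Each required ULN is below the density of water, so no flag is possible in any of these cases. The same holds for any M below 1.100, since M / 1.1 is then below 1.000.

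**Step 3: units.** Reporting the value multiplied by 1000 changes nothing, because the rule is a ratio: 1.1 × 1030 = 1133.

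**Step 4: contrast.** Ten percent applied to the distance above water, 1 + 1.1 × (ULN − 1), would be 1.033 at a ULN of 1.030, just beyond the normal limit. The rule as written gives 1.133. This shows the mismatch of scale only. Nothing in the documents supports 1.033 as a clinically important limit.

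**The case against.** The strongest objection is that the documents do not prove the row must be empty. The anchor at 1.000 proves only that the cut-off is at least 1.100. The further step needs a ceiling on urine readings, which neither document gives, and a data or unit error could still trigger a flag. This stands, so the conclusion is stated as conditional. The condition is a mild one: the result is the same for every ceiling tried, up to 1.080.

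The second objection is that little is lost. The minimum and maximum by time point, and the low/normal/high shift tables, would show a rise in specific gravity in any arm. This also stands. A reader might infer that a urinary safety signal would be hidden, or that the empty row would be taken as evidence of safety. The documents do not support the first, because of those other displays. The second is conjecture, and a row empty in all arms supports no comparison between them.

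A reader might also extend the point to urine pH, which has multipliers in the same table. The documents do not carry it. They give no pH limits, assay method or measuring range, and a logarithmic scale does not by itself put a ratio cut-off out of reach. For the high side, an assumed ULN of 8.0 gives 1.1 × 8.0 = 8.8, and nothing in the documents shows that to be unattainable.

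Finally, it would be wrong to quote zero flags out of 777. That is the approximate number planned for randomization. Safety summaries use the Safety Analysis Set of treated subjects (SAP 4.1 and 10.1), whose size the documents do not give.

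**Conclusion.** The point holds for specific gravity alone. For any ULN of at least 1.000 the cut-off is at least 1.100, and it is 1.122 to 1.144 for an assumed ULN of 1.020 to 1.040. On the assumption that valid urine readings stay below 1.100, the criterion cannot be met. Since there is no low criterion, specific gravity then has no working PCI rule, and its row and listing will be empty in every arm. Nothing else in Appendix B or SAP 10.3 repairs this.

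The consequence is minor: one descriptive row and its listing. Efficacy, error control and sample size are untouched.

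**What to change.** In Table B-3, take one of two courses:

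- Replace the specific gravity criterion with one that fits the scale, for example > ULN, keeping the existing note on the baseline value. The plain-limit form already appears in Table B-2 for low potassium. The cost is that some more subjects may be flagged (the documents do not allow an estimate of how many) and that the flag will largely overlap the high category of the shift table.
- Delete the row and rely on the shift tables and by-visit summaries. The cost is that specific gravity then has no PCI display, which on the assumption above is already the case in effect.

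Either course is an edit to one row of one appendix table, with a matching change to the output program.
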